5.3.3 Assessment of Severity of Adverse Events

The adverse event severity grading scale for the NCI CTCAE (v5.0) will be used for assessing adverse event severity. [Table 3](#) will be used for assessing severity for adverse events that are not specifically listed in the NCI CTCAE.

Table 3 Adverse Event Severity Grading Scale for Events Not Specifically Listed in NCI CTCAE

Grade	Severity
1	Mild; asymptomatic or mild symptoms; clinical or diagnostic observations only; or intervention not indicated
2	Moderate; minimal, local, or non-invasive intervention indicated; or limiting age-appropriate instrumental activities of daily living ^a
3	Severe or medically significant, but not immediately life-threatening; hospitalization or prolongation of hospitalization indicated; disabling; or limiting self-care activities of daily living ^{b, c}
4	Life-threatening consequences or urgent intervention indicated ^d
5	Death related to adverse event ^d

NCI CTCAE = National Cancer Institute Common Terminology Criteria for Adverse Events.

Note: Based on the most recent version of NCI CTCAE (v5.0), which can be found at:
http://ctep.cancer.gov/protocolDevelopment/electronic_applications/ctc.htm

- ^a Instrumental activities of daily living refer to preparing meals, shopping for groceries or clothes, using the telephone, managing money, etc.
- ^b Examples of self-care activities of daily living include bathing, dressing and undressing, feeding oneself, using the toilet, and taking medications, as performed by patients who are not bedridden.
- ^c If an event is assessed as a "significant medical event," it must be reported as a serious adverse event (see Section 5.4.2 for reporting instructions), per the definition of serious adverse event in Section 5.2.2.
- ^d Grade 4 and 5 events must be reported as serious adverse events (see Section 5.4.2 for reporting instructions), per the definition of serious adverse event in Section 5.2.2.

5.3.4 Assessment of Causality of Adverse Events

Investigators should use their knowledge of the patient, the circumstances surrounding the event, and an evaluation of any potential alternative causes to determine whether an adverse event is considered to be related to the study drug, indicating "yes" or "no" accordingly. The following guidance should be taken into consideration (see Table 4):

- Temporal relationship of event onset to the initiation of study drug
- Course of the event, with special consideration of the effects of dose reduction, discontinuation of study drug, or reintroduction of study drug (as applicable)
- Known association of the event with the study drug or with similar treatments
- Known association of the event with the disease under study
- Presence of risk factors in the patient or use of concomitant medications known to increase the occurrence of the event
- Presence of non-treatment-related factors that are known to be associated with the occurrence of the event

Table 4 Causal Attribution Guidance

Is the adverse event suspected to be caused by the study drug on the basis of facts, evidence, science-based rationales, and clinical judgment?	
YES	There is a plausible temporal relationship between the onset of the adverse event and administration of the study drug, and the adverse event cannot be readily explained by the patient's clinical state, intercurrent illness, or concomitant therapies; and/or the adverse event follows a known pattern of response to the study drug; and/or the adverse event abates or resolves upon discontinuation of the study drug or dose reduction and, if applicable, reappears upon re-challenge.
NO	An adverse event will be considered related, unless it fulfills the criteria specified below. Evidence exists that the adverse event has an etiology other than the study drug (e.g., preexisting medical condition, underlying disease, intercurrent illness, or concomitant medication); and/or the adverse event has no plausible temporal relationship to administration of the study drug (e.g., cancer diagnosed 2 days after first dose of study drug).

5.3.5 Procedures for Recording Adverse Events

Investigators should use correct medical terminology/concepts when recording adverse events on the Adverse Event eCRF. Avoid colloquialisms and abbreviations.

Only one adverse event term should be recorded in the event field on the Adverse Event eCRF.

5.3.5.1 Diagnosis versus Signs and Symptoms

A diagnosis (if known) should be recorded on the Adverse Event eCRF rather than individual signs and symptoms (e.g., record only liver failure or hepatitis rather than jaundice, asterixis, and elevated transaminases). However, if a constellation of signs and/or symptoms cannot be medically characterized as a single diagnosis or syndrome at the time of reporting, each individual event should be recorded on the Adverse Event eCRF. If a diagnosis is subsequently established, all previously reported adverse events based on signs and symptoms should be nullified and replaced by one adverse event report based on the single diagnosis, with a starting date that corresponds to the starting date of the first symptom of the eventual diagnosis.

5.3.5.2 Adverse Events That Are Secondary to Other Events

In general, adverse events that are secondary to other events (e.g., cascade events or clinical sequelae) should be identified by their primary cause, with the exception of severe or serious secondary events. A medically significant secondary adverse event that is separated in time from the initiating event should be recorded as an independent event on the Adverse Event eCRF. For example:

- If vomiting results in mild dehydration with no additional treatment in a healthy adult, only vomiting should be reported on the eCRF.
- If vomiting results in severe dehydration, both events should be reported separately on the eCRF.

- If a severe gastrointestinal hemorrhage leads to renal failure, both events should be reported separately on the eCRF.
- If dizziness leads to a fall and consequent fracture, all three events should be reported separately on the eCRF.
- If neutropenia is accompanied by an infection, both events should be reported separately on the eCRF.

All adverse events should be recorded separately on the Adverse Event eCRF if it is unclear as to whether the events are associated.

5.3.5.3 Persistent or Recurrent Adverse Events

A persistent adverse event is one that extends continuously, without resolution, between patient evaluation timepoints. Such events should only be recorded once on the Adverse Event eCRF. The initial severity (intensity or grade) of the event will be recorded at the time the event is first reported. If a persistent adverse event becomes more severe, the most extreme severity should also be recorded on the Adverse Event eCRF. If the event becomes serious, it should be reported to the Sponsor immediately (i.e., no more than 24 hours after learning that the event became serious; see Section 5.4.2 for reporting instructions). The Adverse Event eCRF should be updated by changing the event from "non-serious" to "serious," providing the date that the event became serious, and completing all data fields related to serious adverse events.

A recurrent adverse event is one that resolves between patient evaluation timepoints and subsequently recurs. Each recurrence of an adverse event should be recorded as a separate event on the Adverse Event eCRF.

5.3.5.4 Abnormal Laboratory Values

Not every laboratory abnormality qualifies as an adverse event. A laboratory test result must be reported as an adverse event if it meets any of the following criteria:

- Is accompanied by clinical symptoms
- Results in a change in study treatment (e.g., dosage modification, treatment interruption, or treatment discontinuation)
- Results in a medical intervention (e.g., potassium supplementation for hypokalemia) or a change in concomitant therapy
- Is clinically significant in the investigator's judgment

It is the investigator's responsibility to review all laboratory findings. Medical and scientific judgment should be exercised in deciding whether an isolated laboratory abnormality should be classified as an adverse event.

If a clinically significant laboratory abnormality is a sign of a disease or syndrome (e.g., ALP and bilirubin 5×ULN associated with cholestasis), only the diagnosis (i.e., cholestasis) should be recorded on the Adverse Event eCRF.

If a clinically significant laboratory abnormality is not a sign of a disease or syndrome, the abnormality itself should be recorded on the Adverse Event eCRF, along with a descriptor indicating whether the test result is above or below the normal range (e.g., "elevated potassium," as opposed to "abnormal potassium"). If the laboratory abnormality can be characterized by a precise clinical term per standard definitions, the clinical term should be recorded as the adverse event. For example, an elevated serum potassium level of 7.0 mEq/L should be recorded as "hyperkalemia."

Observations of the same clinically significant laboratory abnormality from visit to visit should only be recorded once on the Adverse Event eCRF (see Section [5.3.5.4](#) for details on recording persistent adverse events).

5.3.5.5 Abnormal Vital Sign Values

Not every vital sign abnormality qualifies as an adverse event. A vital sign result must be reported as an adverse event if it meets any of the following criteria:

- Is accompanied by clinical symptoms
- Results in a change in study treatment (e.g., dosage modification, treatment interruption, or treatment discontinuation)
- Results in a medical intervention or a change in concomitant therapy
- Is clinically significant in the investigator's judgment

It is the investigator's responsibility to review all vital sign findings. Medical and scientific judgment should be exercised in deciding whether an isolated vital sign abnormality should be classified as an adverse event.

If a clinically significant vital sign abnormality is a sign of a disease or syndrome (e.g., high blood pressure), only the diagnosis (e.g., hypertension) should be recorded on the Adverse Event eCRF.

Observations of the same clinically significant vital sign abnormality from visit to visit should only be recorded once on the Adverse Event eCRF (see Section [5.3.5.5](#) for details on recording persistent adverse events).

5.3.5.6 Abnormal Liver Function Tests

The finding of an elevated ALT or AST ($>3 \times$ baseline value) in combination with either an elevated total bilirubin ($>2 \times$ ULN) or clinical jaundice in the absence of cholestasis or other causes of hyperbilirubinemia is considered to be an indicator of severe liver injury (as defined by Hy's Law). Therefore, investigators must report as an adverse event the occurrence of either of the following:

- Treatment-emergent ALT or AST $>3 \times$ baseline value in combination with total bilirubin $>2 \times$ ULN (of which $\geq 35\%$ is direct bilirubin)
- Treatment-emergent ALT or AST $>3 \times$ baseline value in combination with clinical jaundice

The most appropriate diagnosis or (if a diagnosis cannot be established) the abnormal laboratory values should be recorded on the Adverse Event eCRF (see Section 5.3.5.1) and reported to the Sponsor immediately (i.e., no more than 24 hours after learning of the event), either as a serious adverse event or an adverse event of special interest (see Section 5.4.2).

5.3.5.7 Deaths

All deaths that occur during the protocol-specified adverse event reporting period (see Section 5.3.1), regardless of relationship to study drug, must be recorded on the Adverse Event eCRF and immediately reported to the Sponsor (see Section 5.4.2). This includes death attributed to progression of COVID-19.

Death should be considered an outcome and not a distinct event. The event or condition that caused or contributed to the fatal outcome should be recorded as the single medical concept on the Adverse Event eCRF. Generally, only one such event should be reported. If the cause of death is unknown and cannot be ascertained at the time of reporting, "**unexplained death**" should be recorded on the Adverse Event eCRF. If the cause of death later becomes available (e.g., after autopsy), "unexplained death" should be replaced by the established cause of death. The term "**sudden death**" should not be used unless combined with the presumed cause of death (e.g., "sudden cardiac death").

If the death is attributed solely to progression of COVID-19, "COVID-19 progression" should be recorded on the Adverse Event eCRF.

Deaths that occur after the adverse event reporting period should be reported as described in Section 5.6.

5.3.5.8 Preexisting Medical Conditions

A preexisting medical condition is one that is present at the screening visit for this study. Such conditions should be recorded on the General Medical History and Baseline Conditions eCRF.

A preexisting medical condition should be recorded as an adverse event only if the frequency, severity, or character of the condition worsens during the study.

When recording such events on the Adverse Event eCRF, it is important to convey the concept that the preexisting condition has changed by including applicable descriptors (e.g., "more frequent headaches").

5.3.5.9 Lack of Efficacy or Worsening of COVID-19

Medical occurrences or symptoms of deterioration that are anticipated as part of COVID-19, such as fluctuations in symptoms, should not be recorded as adverse events. However, deterioration that is judged by the investigator to have unexpectedly worsened in severity or frequency or changed in nature at any time during the study should be recorded as an adverse event. When recording an unanticipated worsening

of COVID-19 on the Adverse Event eCRF, it is important to convey the concept that the condition has changed by including applicable descriptors (e.g., accelerated worsening of COVID-19). Any COVID-19-related medically attended visits (defined as hospitalization, ER visit, urgent care visit, physician's office visit, or telemedicine visit, with the primary reason for the visit being COVID-19) should be reported in the eCRF (see Section 4.5.6.3).

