Nonclinical and clinical safety studies have not revealed any pattern of drug-attributable adverse effects or any consistent clinically significant laboratory abnormalities related to any body system. Repeat dose-toxicity studies of up to 13 weeks duration in rats and monkeys did not show target organ toxicity up to the highest tested dose levels. In rats, the no-observed-adverse effect level (NOAEL) was the highest tested dose at 1000 mg/kg/day in these studies. In monkeys, the NOAEL in a 7-day study was 1000 mg/kg/day, a dose that was reduced to 650 mg/kg/day on Day 8 of a 14-day study due to loose stools, emesis, inappetence, and weight loss. The dose level of 650 mg/kg/day was the NOAEL and the highest tested dose in a subsequent 13-week monkey toxicity study. Plasma exposures achieved in these studies either exceeded or approximated the anticipated clinical exposures for the different metabolites in one or both species, depending on the metabolite. The potential for reproductive toxicity was assessed in dose, range-finding, and pivotal Good Laboratory Practice (GLP)-compliant embryofetal development studies in rats and rabbits and in a GLP-compliant fertility study in the rat. These studies have not revealed a concern for reproductive toxicity and achieved exposures that exceeded the anticipated clinical exposures (see [Appendix 7](#)). Thus, the nonclinical safety data are considered to be supportive of the intended clinical dose levels and regimens and consistent with international guidelines, ICH Topic M3 (R2) and associated question and answer document (ICH 2008; ICH 2012). The

potential for gastrointestinal effects in humans will be monitored by means of medical data review and safety review on an ongoing basis in this study.

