5.3.5.12 Patient-Reported or Observer-Reported Outcome Data

Adverse event reports will not be derived from PRO data by the Sponsor. Sites are not expected to review the PRO data for adverse events.

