Appendix 4 COVID-19 Symptom Diary

Do not reproduce or distribute. The Sponsor will provide sites with all instruments to be completed in this study.

Note that the following is a sample. Sites will be provided with separate versions of the diary, reflecting appropriate recall periods.

COVID-19 Symptom Diary (Morning)

This diary will keep track of your COVID-19 symptoms and temperature during the study. Please complete this diary when you first wake up in the morning (before getting out of bed). Remember to take your temperature before you take any medicines to help your COVID-19 symptoms.

Please rate the severity of each symptom at its worst since you went to bed last night.

	None 0	Mild 1	Moderate 2	Severe 3
1. Nasal Congestion or runny nose				
2. Sore Throat				
3. Cough				
4. Shortness of breath (difficulty breathing)				
5. Muscle or body aches				
6. Fatigue (tiredness)				
7. Headache				
8. Chills/Sweats				
9. Feeling hot or feverish				
10. Nausea (wanting to throw up)				
11. Vomiting (thrown up)				
12. Diarrhea (mostly or completely liquid bowel movements)				

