5.4.4 Supportive Secondary Safety Endpoints

5.4.4.1 Incidence of Adverse Events

Descriptive summaries of treatment-emergent adverse events will be presented.

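### Gastrointestinal safety based on recorded adverse events will probably be under-ascertained, and the SAP has no between-arm safety summary of new or worsened nausea, vomiting or diarrhea from the diary

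*Protocol*

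**What the plan says.** **The commitment.** Protocol 1.3 reports that a dose in a monkey study was lowered "due to loose stools, emesis, inappetence, and weight loss". It then states that the "potential for gastrointestinal effects in humans will be monitored by means of medical data review and safety review on an ongoing basis". The protocol names no terms, method or output for doing this.

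**The same symptoms as disease.** Protocol 1.1 lists gastrointestinal disturbance among the common symptoms of COVID-19, and 3.3.2 includes gastrointestinal symptoms in the definition of mild disease. In 4.1.1, nausea, vomiting and diarrhea count towards eligibility. They are diary Items 10 to 12 (Appendix 4), the last being "12. Diarrhea (mostly or completely liquid bowel movements)".

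**The recording rule.** Protocol 5.3.5.9 says that "symptoms of deterioration that are anticipated as part of COVID-19, such as fluctuations in symptoms, should not be recorded as adverse events". The next sentence makes an exception, to be recorded as an adverse event: "deterioration that is judged by the investigator to have unexpectedly worsened in severity or frequency or changed in nature at any time during the study".

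**The diary.** It is completed twice daily on Days 1-14 and daily to Day 29. Under 5.3.5.12 the sponsor derives no adverse events from it, and "Sites are not expected to review the PRO data for adverse events".

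**The analysis.** SAP 5.4.4.1 reads: "Descriptive summaries of treatment-emergent adverse events will be presented". SAP 5.1 tabulates adverse events by system organ class and preferred term. SAP 5.6.2 adds tables by onset (including Days 1-7), by discontinuation and by suspected causality. All of these start from recorded events. SAP 5.4.2.2 analyses single diary symptoms, but only in patients with a baseline score of at least 2.

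**The concern.** A drug effect on the gut would look like the disease. A blinded investigator who hears of mild or moderate diarrhea on Day 2 has no stated basis for calling it unexpected, and the default in 5.3.5.9 is then not to record it. Questioning is non-directive (5.3.2), so nothing prompts for these symptoms. The instrument that does capture them twice a day, in both blinded arms, feeds the efficacy analyses and no safety output described in the SAP.

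At stake is the secondary safety objective, as it applies to gastrointestinal tolerability. If sites record few of these symptoms, the tables can show a small absolute difference when the real one is larger. There is also a link to efficacy. A new moderate or severe Item 10-12 symptom that appears before the primary endpoint is met delays that endpoint (SAP 5.3.1), so a tolerability problem could show up partly as lost efficacy.

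**Working it through.** The plan gives no gastrointestinal event rate and no test of adverse events, so there is no figure of its own to reproduce. The check is a reading of the text, followed by an illustration.

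**Reading: where would new moderate diarrhea on Day 2 appear, in a patient without diarrhea at baseline?**

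| Output | Does it show? |
|---|---|
| Adverse event tables (SAP 5.4.4, 5.6.2) | Only if the investigator records it, i.e. does not treat it as anticipated under 5.3.5.9 |
| Adverse events of special interest | No; the list is potential liver injury and suspected transmission of an infectious agent |
| Time to alleviation of diarrhea (SAP 5.4.2.2) | No; baseline score is below 2 |
| Primary endpoint (SAP 5.3.1) | Only as a delay in an efficacy event |
| Laboratory values and vital signs | Not directly |

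Inappetence and weight loss, the other monkey findings, are not diary items, and weight is scheduled at screening only (Protocol 4.5.3, Appendix 1).

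**Illustration: what under-recording does to a real difference.**

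Inputs from the documents: 1386 patients randomized 2:1, so 1386 × 2/3 = 924 active and 462 placebo, taking all as dosed.
Assumptions: true rates p1 (active) and p0 (placebo) of new gastrointestinal symptoms during dosing, and a recording fraction r that is the same in both arms.

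Expected z = r(p1 − p0) / √[r·p1(1 − r·p1)/924 + r·p0(1 − r·p0)/462].

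For p1 = 15%, p0 = 10%, r = 1: 0.05 / √(0.15 × 0.85/924 + 0.10 × 0.90/462) = 0.05/0.01824 = 2.74.

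| r | Recorded rates | Difference (points) | Ratio | Expected z |
|---|---|---|---|---|
| 100% | 15% v 10% | 5.0 | 1.5 | 2.74 |
| 50% | 7.5% v 5% | 2.5 | 1.5 | 1.87 |
| 20% | 3% v 2% | 1.0 | 1.5 | 1.16 |
| 10% | 1.5% v 1% | 0.5 | 1.5 | 0.82 |

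To show the range over assumed rates, the next table gives power at two-sided 0.05, as Φ[(d − 1.96·SE0)/SE1]. Here d is the recorded difference, SE0 its pooled standard error and SE1 its unpooled standard error.

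| True rates | r = 100% | 50% | 25% | 10% |
|---|---|---|---|---|
| 10% v 5% | 0.912 | 0.604 | 0.318 | 0.133 |
| 15% v 10% | 0.745 | 0.415 | 0.215 | 0.101 |
| 20% v 10% | 0.999 | 0.912 | 0.604 | 0.255 |

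No such test is planned. Power is used here only as a measure of how clearly a difference would stand out.

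**The diary is not a perfect measure either.** From Day 1 bedtime to Day 7 there are 1 + 6 × 2 = 13 expected post-dose entries, and a one-category rise on any of three items will also pick up the disease itself. If that background were 25%, 35% or 45% in the placebo arm, with the same 5-point excess on active, the unpooled z would be 1.99, 1.82 or 1.76. The 35% case is close to the 50%-recording row above. The diary therefore has a clear advantage only where recording is well below half, or where the measure is strict (reaching 2 or more from 0-1).

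**The case against.** The best case for the plan is that it leaves more room than the default rule suggests. The exception in 5.3.5.9 covers worsening judged unexpected or changed in nature, and new diarrhea in a patient without gut symptoms could be read that way. Protocol 5.2.1 defines an adverse event without regard to causality, and 5.3.5.2 itself uses vomiting as an example of a reportable event. The SAP tables by organ class and by onset in Days 1-7 would show recorded gastrointestinal events by arm during dosing. The iDMC charter and the table specifications are separate documents that have not been seen and may contain more. All of this stands, and it limits the point. It does not supply an analysis of symptoms that went unrecorded.

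Four stronger inferences are tempting, and the documents do not support them:

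- *Gastrointestinal effects are the only toxicity under watch.* Potential drug-induced liver injury is an adverse event of special interest (5.2.3), and CK, amylase, lipase and creatinine are measured (4.5.5).
- *Sites are forbidden to look at the diary or to record gut symptoms.* Section 5.3.5.12 says only that review is not expected, and 5.3.5.9 turns on judgement.
- *The safety question cannot be answered.* The needed data are collected in a randomized, blinded design. What is missing is a planned summary.
- *Any new gut symptom holds up the primary endpoint.* A new mild symptom meets the criterion (SAP 5.3.1). For moderate or severe ones, SAP 5.3.3 already plans a sensitivity analysis restricted to baseline presenting symptoms, although it is not specific to Items 10-12.

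**Conclusion.** The point holds in a limited form. Mild or moderate nausea, vomiting or diarrhea that starts on treatment will probably be under-recorded as adverse events, and no analysis in the SAP recovers it from the diary. The monitoring commitment in Protocol 1.3 has no specific output behind it.

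The size cannot be fixed from the documents. Under the assumed rates, recording half of events halves the absolute difference and takes the expected z from 2.74 to 1.87; recording a tenth takes it to 0.82. With equal under-recording the ratio between arms is unchanged, so the comparison is weakened, not reversed or made impossible. These figures assume the same recording fraction in both arms, which blinding makes reasonable but does not guarantee. This is an inexpensive improvement to the safety analysis and does not affect the validity of the trial.

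**What to change.** Add one descriptive table to SAP 5.6, on the safety-evaluable set by treatment received, for Day 1 post-dose to Day 7. For each of Items 10, 11 and 12, and for any of the three, give:

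- the proportion reaching a score of 2 or more from a pre-dose score of 0-1;
- the proportion rising at least one category above the pre-dose score;
- the difference between arms with a 95% CI, and the denominators.

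Use observed item scores. SAP 5.1.1 sets a missing item to the highest score when other items are present, which would create false gastrointestinal events here. Make the table available to the iDMC.

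The cost is one table from data already collected. The measure also captures disease fluctuation in both arms, so it should be read as a contrast between arms and not as a rate of drug effects.

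Protocol 5.3.5.9 and the commitment in 1.3 should also be reconciled, so that sites know how gastrointestinal symptoms starting after the first dose are to be handled. Requiring every such symptom to be recorded as an adverse event is not proposed. It would fill the tables with disease events, a trade-off that is for the sponsor to judge.
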